5.3.5.3 Device Failure Criteria

The device failure criteria provided by the surgeon will be summarized as frequency (N) and percentage (%) by scheduled visit.

Other surgeon reported outcomes may be input to the database. These possible outcomes will be summarized as appropriate using descriptive summary characteristics for continuous or categorical endpoints. Differences from screening/baseline to 6 months and 12 months will be similarly summarized.

5.3.6 Safety Analysis

All safety endpoints will be summarized using the FAS. The adverse events (AEs) will be coded using the internal Smith + Nephew coding dictionary.

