## 7.7 LOST TO FOLLOW-UP

A subject will be considered lost to follow-up if he/she did not return for follow-up per the Investigator's standard of care follow-up schedule. Information will be documented on the Case Report Form (CRF).

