3.2 Identification of Analysis Populations

3.2.1 Full Analysis Set

The Full Analysis Set (FAS) includes all subjects enrolled in the study who had previously undergone arthroscopic repair using the MINITAC[◇] Ti 2.0 Suture Anchor. The FAS will be used for the analysis of all measures and endpoints.

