5.2 General Presentation Considerations

As this study is of a descriptive nature, the analysis results will be reported using descriptive statistics.

Continuous data will be summarized in terms of the mean, standard deviation (SD), median, minimum, maximum and number of observations, unless otherwise stated. Continuous data that are expected to be skewed will be presented in terms of the maximum, upper quartile, median, lower quartile, minimum and number of observations. The minimum and maximum will be reported to the same number of decimal places as the raw data recorded in the database. The mean, median, lower quartile and upper quartile will be reported to one more decimal place than the raw data recorded in the database. The SD will be reported to two more decimal places than the raw data recorded in the database. In general, the maximum number of decimal places reported shall be four for any summary statistic.

Categorical data will be summarized in terms of the number of subjects providing data at the relevant time point (n), frequency counts and percentages. Percentages will be presented to one decimal place. Percentages will not be presented for zero counts. Percentages will be calculated using n as the denominator.

Given the small, convenience study sample, as well as the absence of *a priori* statistical hypotheses, no formal tests of statistical significance are planned, and as such, no p-values or statistical intervals will be calculated.

All report outputs will be produced using SAS[®] version 9.3 or a later version in a secure and validated environment. All report outputs will be provided to the Sponsor as individual .rtf files and as a consolidated .pdf document.

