5.3.2 Analysis of the Primary Endpoint

The proportion of subjects with clinical success at 6 months post operation (182 days + 30 / -150 days) will be summarized with a frequency and percentage. Clinical success is achieved only if all of the following are true for a patient (as indicated by the items in the impact status form in the study case report form):

- Did not experience any inflammation;
- Did not have any device related AEs;
- Did not have any device deficiencies;
- Did not experience any device failure (malfunction);
- Did not have any signs of repair failure, and;
- Did not undergo any re-intervention.

Subgroup (defined in section 3.3) corresponding proportions will be presented in tabular form. All analyses will be carried out using the FAS.

In addition, the primary endpoint will also be estimated for +/- 3 months (3-9 month window) as per standard of care.

Incidence rates of the post-operative device failure and/or device related re-intervention at 6 months will be estimated. Specifically, the following will be summarized and estimated:

- The number of patients at risk of an event;
- The number of patients with events;
- The number of events;
- Total person-months;
- Crude rate/person-months;
- Estimated rate.

Person-months are months for each patient between baseline and 6 months included in the FAS. The estimated rate will be derived using Poisson regression with an offset as (the log of) the duration at risk for each patient.

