5.3.6.2 AE Analysis

All AEs and complications occurring from the time of subject enrollment until study termination or study completion including intra-operative AEs and complications, will be summarized by coded term, and by action taken.

An overall summary table of AEs, ADEs, SAEs, SADEs, USADEs, ASADEs, AEs leading to death, AEs leading to permanent impairment, removal/revision, DD, device failure and participation discontinuation will be presented. For each AE, the percentage of subjects who experience ≥ 1 occurrence of the given event will be summarized. The same summary will be provided for SAEs, SADEs, USADEs, ASADEs, as well as AEs leading to death, a permanent impairment of a body structure or body function, removal/revision, DD, device failure or study participation discontinuation.

AE summaries will be ordered in terms of decreasing frequency, and then alphabetically for the coded terms by Nonoperative Site Systemic Codes, or Operative Site Codes and associated sub-categories (if provided).

For each subject and each AE, the worst severity recorded will be attributed and used in the by-severity summaries. Similarly, the worst causality (most related to IP or the procedure) will be attributed and used in the by-causality summaries. As an exception, AEs that have missing causality (after data querying) will be assumed to be related to study drug.

By-subject listing of all AEs will be provided. The listings will include: subject identifier, adverse event (coded term), Nonoperative or Operative Site Codes and associated sub-categories (if provided), start/end dates and corresponding study day, relatedness to IP or procedure, seriousness, anticipated or not, leading to death, removal/revision or DD, leading to study participation discontinuation and other information. Additional summaries or listings may be provided, as appropriate.

Implant status collected will also be summarized by scheduled visit.

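### The adverse event tables give only the percentage of FAS subjects with an event and take no account of how long each chart was observed, so they cannot be read as 12-month incidence.

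*SAP*

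**What the plan says.** **Analysis set.** SAP 3.2.1 defines the FAS as all enrolled subjects who had the repair, and adds: "The FAS will be used for the analysis of all measures and endpoints". SAP 5.3.6 applies this to safety: "All safety endpoints will be summarized using the FAS".

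**AE measure.** SAP 5.3.6.2 says: "For each AE, the percentage of subjects who experience ≥ 1 occurrence of the given event will be summarized". The serious categories are treated the same way, and adverse device effects (ADEs) appear in the overall table. The tables run to study completion and are not split by visit. Re-interventions and device deficiencies, by contrast, are summarized by scheduled visit (SAP 5.3.6.3 and 5.3.6.4).

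**Denominator rule.** SAP 5.2 reports categorical data by the "number of subjects providing data at the relevant time point (n), frequency counts and percentages", and then says: "Percentages will be calculated using n as the denominator".

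**Exposure elsewhere.** For device failure and device-related re-intervention, the list in SAP 5.3.2 opens with "The number of patients at risk of an event". It continues with subjects with events, events, person-months, a crude rate and a Poisson estimate. SAP 5.3.3 repeats this at 12 months and adds a Kaplan-Meier analysis of time to first event, with censoring at the latest assessment.

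**Follow-up.** The footnote to Protocol Table 9.1-1 limits collection to what the chart contains. Protocol 7.2 requires that surgery was more than 12 months ago, but no minimum follow-up. Protocol 7.7 says: "A subject will be considered lost to follow-up if he/she did not return for follow-up per the Investigator's standard of care follow-up schedule". SAP 5.6 rules out imputation.

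**The concern.** A percentage of subjects with an event estimates 12-month risk only if each subject was observed for 12 months or had the event first. Here a chart may end weeks after surgery, and that subject still counts in the FAS. Later events, if any, are unseen and add nothing to the numerator.

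Safety is named in both study objectives, so these tables carry much of the report. Some harm can come late: in Protocol 4.2, a cited foot-and-ankle series describes a suture excised for scar tenderness at 9 months. The SAP also handles unequal follow-up properly for one class of event and not for the other, without giving a reason.

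**Working it through.** **No figure to reproduce.** The documents state no AE rate, loss rate or event timing. Their only computed figures, 55.4% and 98.8%, concern the precision of the success rate and do not enter here.

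**Step 1: does SAP 5.2 settle the denominator?** It defines n as subjects with data at a time point. The AE tables span the whole period and have no single time point. AE records exist only where an event occurred, so n cannot be counted from them. The FAS is therefore the natural denominator, but the SAP does not say so.

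**Step 2: how much hangs on that choice?** Suppose 3 subjects have an event, all among subjects with data (assumed counts).

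| FAS size | 3 / FAS | 10% without data | 20% without data | 40% without data |
|---|---|---|---|---|
| 30 | 10.0% | 3/27 = 11.1% | 3/24 = 12.5% | 3/18 = 16.7% |
| 50 | 6.0% | 3/45 = 6.7% | 3/40 = 7.5% | 3/30 = 10.0% |

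**Step 3: how far does the FAS percentage fall below 12-month risk?** Let q be the true 12-month risk, d the share of charts that stop early, s the stopping time in months and F(s) the risk by s. Events before the stop are counted, so

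expected FAS percentage = (1 − d)·q + d·F(s).

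Assumptions, none taken from the documents:
- q = 10%, and d = 10%, 20% or 40%.
- Charts stop at day 32 (182 − 150, the first day of the 6-month window; 32/30.4375 = 1.05 months) or at 6 months.
- Subjects whose charts stop have the same risk as the others.
- Timing A, constant hazard: F(s) = 1 − (1 − q)^(s/12).
- Timing B, 80% of events in month 1 and the rest spread evenly: F(s) = q·(0.8 + 0.2·(s − 1)/11).

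Example (A, day 32, d = 40%): F = 1 − 0.9^(1.05/12) = 0.0092, and 0.6 × 0.10 + 0.4 × 0.0092 = 0.0637. The understatement is 1 − 0.0637/0.10 = 36%.

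| Timing | Charts stop at | d = 10% | d = 20% | d = 40% |
|---|---|---|---|---|
| A | day 32 | 9.1% | 8.2% | 6.4% |
| A | 6 months | 9.5% | 9.0% | 8.1% |
| B | day 32 | 9.8% | 9.6% | 9.2% |
| B | 6 months | 9.9% | 9.8% | 9.6% |

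Against a true 10%, the relative understatement runs from about 1% (B, 6 months, d = 10%) to 36% (A, day 32, d = 40%). Under A it is almost the same at true risks of 5% and 20%: the worst-case ratios are 0.636 and 0.639.

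**Step 4: in subjects.** The worst case is (0.10 − 0.0637) × 30 = 1.1 subjects, or × 50 = 1.8 subjects. With d = 20% and stops at day 32 under A, it is (0.10 − 0.0818) × 50 = 0.9 subjects.

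**Step 5: do the disposition counts fill the gap?** SAP 5.4.1 counts completed 6- and 12-month visits. The windows of +30/−150 days run from day 32 to 212 and from day 215 (365 − 150) to 395. A subject last seen at day 215 can count as having completed the 12-month visit with about 7 months observed, so these counts do not show follow-up to the end of the period.

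**The case against.** The strongest reply is that SAP 5.3.6 names an analysis set, not a denominator. Clinical success is also analysed on the FAS, and the n rule in SAP 5.2 covers all categorical data. No sentence says that unfollowed subjects count as event-free. This stands as far as it goes: the full-FAS denominator is an inference. But n has no clear meaning for these tables, so the SAP needs a sentence on either reading.

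Second, the study is descriptive, and subject percentages with counts and dated listings are a legitimate presentation. Visit dates and disposition are already reported, and device failure and re-intervention already have person-time and censoring. This limits the harm. It does not give the reader of the AE table the observed follow-up.

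Third, the size rests on assumed inputs. If events cluster around surgery the shortfall is a few per cent, and if subjects who stopped returning had no later events it is nil. A crude person-month rate can mislead too when the hazard is not constant, because short charts then add events but little time. Both points stand, and they are why the percentage should be kept and a Kaplan-Meier estimate added.

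A reader might go further and infer that the ADE percentage contradicts the success rate, since freedom from device-related AEs is one component of success in SAP 5.3.2. The documents do not support that. ADEs in SAP 5.3.6.1 include procedure-related events, the AE tables run to study completion while success is read at 6 or 12 months, and different denominators are only one possible reading.

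**Conclusion.** The point holds as an improvement to the planned tables. AE, ADE, SAE and SADE percentages on the FAS describe events found in the charts; they are not 12-month incidence. If the FAS is the denominator, the percentage cannot exceed the true proportion of subjects with an event, so any error in it from unobserved time is downward. Its size is unknown: about 1% to 36% relative under the stated assumptions, or at most about one to two subjects at the planned sample sizes when the true risk is 10%.

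Two stronger readings should be avoided. Subjects with short charts are not all scored event-free; only the unobserved part of their follow-up is. Nor do the documents show that the harm rates will be materially too low: they give no loss rate, and Protocol 4.2 mentions loosening and migration without saying when they occur.

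**What to change.** In SAP 5.3.6.2:

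- State that the denominator of the AE percentages is the FAS. Keep the percentage, and label it as observed events, not 12-month incidence.
- Beside it, give subjects at risk, subjects with events, number of events, person-months from operation to last chart entry (counting only time in which AEs were collected) and the crude rate, as in SAP 5.3.2.
- Give the number of subjects whose chart follow-up actually reaches 6 and 12 months.
- Because a crude rate assumes a roughly constant hazard, add Kaplan-Meier estimates of time to first AE, first device-related AE and first SAE, censored at the last assessment as in SAP 5.3.3. SAP 5.8 sets Kaplan-Meier aside for the 6- and 12-month device event rates, so record this addition there. It can stay descriptive, without intervals.

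Do not restrict ADEs to subjects evaluable for success: that could drop intra-operative events in subjects with no later data.

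The cost is SAP wording, a few table columns and slightly less favourable rates. The dates are already needed for SAP 5.3.2 and 5.3.3. Kaplan-Meier assumes that subjects whose charts stop resemble those who remain, which the report should say.

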5.3.6.1 Definition of AE Categories

The definitions for each of the AE categories are based on ISO 14155:2011 [2].

An AE is any untoward medical occurrence, unintended disease or injury, or untoward clinical sign (including abnormal laboratory findings) in subjects, users or other persons, whether or not it is related to the investigational product (IP) or the procedure.

An Adverse Device Effect (ADE) is an AE that is possibly, probably or definitely related to the use of the investigational product (IP) or the procedure.

An AE or ADE is considered a Serious Adverse Event (SAE) or Serious Adverse Device Effect (SADE) if, in the view of either the Investigator or the Sponsor, the event:

- a) led to death,
- b) led to serious deterioration in the health of the subject, that either resulted in
 - a life-threatening illness or injury, or
 - a permanent impairment of a body structure or a body function, or
 - in-patient or prolonged hospitalization, or
 - medical or surgical intervention to prevent life-threatening illness or injury or permanent impairment to a body structure or a body function,
- c) led to fetal distress, fetal death or a congenital abnormality or birth defect.

Planned hospitalization for a pre-existing condition, or a procedure required by the study protocol, without serious deterioration in health, is not considered a serious adverse event.

An Unanticipated Serious Adverse Device Effect (USADE) is a serious ADE which by its nature, incidence, severity or outcome has not been identified in the current version of the risk analysis report. On the other hand, anticipated serious adverse device effect (ASADE) is an effect which by its nature, incidence, severity or outcome has been identified in the risk analysis report.

The severity of every AE will be assessed by the Principal Investigator (PI) or medically qualified site staff to whom the responsibility has been delegated and documented on the delegation of authority log. AE should be classified as mild, moderate, or severe, regardless of whether or not the AE are considered to be serious or non-serious.

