**Table 12.1-1: Categories of Adverse Event**

	NOT DEVICE-RELATED	DEVICE- OR PROCEDURE-RELATED	
NON-SERIOUS	ADVERSE EVENT (AE)	ADVERSE DEVICE EFFECT (ADE)	
SERIOUS	SERIOUS ADVERSE EVENT (SAE)	SERIOUS ADVERSE DEVICE EFFECT (SADE) (SEE 12.1.3)	
		ANTICIPATED	UNANTICIPATED
		ANTICIPATED SERIOUS ADVERSE DEVICE EFFECT (ASADE)	UNANTICIPATED SERIOUS ADVERSE DEVICE EFFECT (USADE)

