### 12.1.2 Adverse Device Effect

An Adverse Device Effect (ADE) is an adverse event related to the use of the IP.

Note 1: This definition includes adverse events resulting from insufficient or inadequate instructions for use, deployment, implantation, installation or operation, or any malfunction of the investigational medical device.

Note 2: This definition includes any event resulting from use error or from intentional misuse of the investigational medical device.

To differentiate between events that are related to the IP and events that are not related to the event the following notes should be taken into consideration:

- **Not Related:** An AE is considered to be not related to the use of an IP or the procedure when the effect is DEFINITELY UNRELATED or UNLIKELY to have any relationship to the use of the IP or the procedure;
- **Related:** An AE is considered to be related to the use of an IP or the procedure when there is a POSSIBLE, PROBABLE, or DEFINITE relationship between the AE and the use of the IP or the procedure.

An ADE is further categorized depending on whether the criteria in section 12.1.3 and 12.1.4 are met.

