## 12.3 REPORTING PROCEDURES

AE of any kind and DD will be identified from the source notes and recorded in the applicable CRF. The Investigator will evaluate all AE for relationship to the device and procedure, if applicable, seriousness, and severity. The following timescales should be followed for the AE/DD information to be entered into the CRF and reported to the Sponsor or designee (see Figure 12.3.1 and Figure 12.3.2):

- ADE and DD – without unreasonable delay
- SAE, SADE and DD with potential to cause SADE – immediately (i.e. within 24 hours of the investigator being informed about the event)

For ADE and DD, details of the product/procedure related to the event will be included and where applicable, pictures taken of the device. The deficient product should be retained for return to S&N, if applicable, unless it is contaminated (e.g., used dressings must not be retained). Updates to submitted information will be recorded in the CRF according to the timescales above.

[figure not shown]
All adverse events will be reviewed by a medically qualified person appointed by the Sponsor to determine which, if any, meet criteria for expedited reporting to the regulatory authorities.

Study Protocol—Device	
Safety and Performance of MINITAC® Ti 2.0 Suture Anchor in Extremities	Number: MINI.PMCF.2018.11
	Version: 3.0, 20Aug19
	Page: Page 35 of 56

The Investigator will inform the HREC/EC of adverse events according to the HREC/EC requirements.

Depending on the nature of the adverse event, the Sponsor may request copies of the subject's medical records, imaging, operative notes, as well as results of any relevant laboratory tests performed or other documentation related to the AE. If the subject was hospitalized, a copy of the discharge summary may be requested by the Sponsor and should be forwarded as soon as it becomes available. In certain cases, the Sponsor also may request a letter from the Investigator that summarizes the events related to the case.

Figure 12.3-1: Evaluation and Reporting of AE

Red path – accelerated reporting within 24 hours  
 Purple path – reporting without unreasonable delay

[figure not shown]
Study Protocol—Device	
Safety and Performance of MINITAC ® Ti 2.0 Suture Anchor in Extremities	Number: MINI.PMCF.2018.11
	Version: 3.0, 20Aug19
	Page: Page 37 of 56

Figure 12.3-2: Evaluation and Reporting of DD

Red path – accelerated reporting within 24 hours

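### The protocol defines an adverse device effect in two ways; the SAP takes the broader one and pools causality, so no planned summary isolates events related to the anchor itself

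*SAP*

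**What the plan says.** **Protocol.** Section 12.1.2 opens with "An Adverse Device Effect (ADE) is an adverse event related to the use of the IP" and does not mention the procedure. Further down, the same section says: "An AE is considered to be related to the use of an IP or the procedure when there is a POSSIBLE, PROBABLE, or DEFINITE relationship". Table 12.1-1 places ADE, SADE, ASADE and USADE under a column headed "DEVICE- OR PROCEDURE-RELATED". Section 12.1.1, on its natural reading, keeps the narrow sense of AE for non-serious events related to neither product nor procedure. On assessment, section 12.3 says "The Investigator will evaluate all AE for relationship to the device and procedure", with an if-applicable qualifier.

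**SAP.** Section 5.3.6.1 puts the procedure into the definition itself: an ADE is an AE "possibly, probably or definitely related to the use of the investigational product (IP) or the procedure". Section 5.3.6.2 plans an overall table with ADE, SADE, USADE and ASADE rows. For the by-causality summaries, "the worst causality (most related to IP or the procedure) will be attributed". It also plans a by-subject AE listing that includes relatedness. The success rule in 5.3.2 has among its six items "Did not have any device related AEs"; it does not use the term ADE and does not refer to 5.3.6.1. Section 5.8, which lists changes from the protocol, does not mention the ADE definition.

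**The concern.** The objective is the safety and performance of one device, for a Notified Body, in a single-arm series of 30 to 50 subjects. With no comparator, nothing in the data shows how often the same complications follow this surgery without the anchor. The only tool for separating the two is the investigator's causality judgement, and the planned summaries combine the two halves of that judgement.

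A reader who sees an ADE or USADE count will take it as a statement about the anchor. Under the SAP definition it is a statement about the anchor or the operation. USADE is the most exposed row: a serious event related only to the operation, and not named in the risk analysis report, would be tabulated as an unanticipated device effect.

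**Working it through.** The documents give no figure on this point, so the check sets the definitions side by side and follows one kind of event through them.

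**Step 1. Classify an event related to the procedure but not to the product.**

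| Source | Non-serious | Serious, in the risk report | Serious, not in the risk report |
|---|---|---|---|
| Protocol 12.1.2, opening sentence | AE | SAE | SAE |
| Protocol 12.1.2, relatedness note | related, so ADE if the note governs | ASADE | USADE |
| Protocol Table 12.1-1 | fits both columns | fits both columns | fits both columns |
| SAP 5.3.6.1 | ADE | ASADE | USADE |

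The table cannot settle the matter. Its other column is headed as not device-related, and a procedure-only event meets that heading as well as "DEVICE- OR PROCEDURE-RELATED". The two headings are not mutually exclusive.

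**Step 2. Ask whether the pooled causality can be undone.** Let r(IP) and r(proc) be the two relationships on the protocol's scale, from definitely unrelated through unlikely, possible and probable to definite. The SAP rule attributes

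pooled = the more related of r(IP) and r(proc).

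If r(proc) is definite, pooled is definite whatever r(IP) is. A pooled value of definite is therefore compatible with every value of r(IP), and the device relationship cannot be recovered from the summary.

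**Step 3. Look for another route to the device-only figure.** The overall table has separate rows for removal or revision, device deficiency and device failure, and SAP 5.3.6.3 and 5.3.6.4 summarise re-interventions and deficiencies. These are device-specific, but none of them counts adverse events related to the product. The by-subject listing shows relatedness but is not a summary.

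**Step 4. Missing causality.** SAP 5.3.6.2 treats missing causality as related to study drug. The study has no drug, so the rule does not say which relationship such an event is assigned to.

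**Step 5. Scale.** Let k be the number of subjects whose only related events are procedure-only. The ADE percentage under the SAP definition exceeds that under the opening sentence of 12.1.2 by k/n. The value of k is not in the documents; the range below is an assumption.

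| k | n = 30 | n = 50 |
|---|---|---|
| 1 | 1/30 = 3.3 points | 1/50 = 2.0 points |
| 2 | 2/30 = 6.7 points | 2/50 = 4.0 points |
| 3 | 3/30 = 10.0 points | 3/50 = 6.0 points |

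**The case against.** The strongest reply is that the SAP did not depart from the protocol. The table heading, section 12.1.1 and the relatedness note all include the procedure, and SAP 5.3.6.1 is close to a restatement of that note. A reader might infer that a narrow protocol definition was widened in the SAP; the documents do not support that. This part of the reply stands. What remains is that the protocol conflicts with itself, and that the SAP chose a side without recording it.

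Second, pooling is cautious for device safety, and the listing lets a reader separate 30 to 50 subjects by hand. Both are true. But caution is a reason to keep the pooled row, not to make it the only row, and a listing leaves the key classification to each reader. One could also read the worst-causality rule as working across repeat occurrences, separately for each relationship; the text attributes a single value and commits to no such split.

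Third, a reader might go further and conclude that the primary success rate is understated. For example, one could take the 6% minor-complication rate in protocol 4.2, treat it as procedure-only and subtract it from the assumed 95%, giving 89%. The documents do not support that figure:

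- The success item says "Did not have any device related AEs". On its plain words it is already device-only, and it draws on a case report form that is not among the documents.
- The 6% comes from one ankle series, while the study also covers elbow, wrist and hand. Nothing says those events were procedure-only.
- Four of the six points are superficial wound infection. If infection is recorded as inflammation, such subjects would fail the separate inflammation item however an ADE is defined.

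**Conclusion.** The point holds as a reporting defect with an unresolved definition behind it. Protocol 12.1.2 conflicts with Table 12.1-1 and with its own later note. The SAP adopts the broader reading and pools causality. The ADE-family and by-causality summaries therefore cannot show what is attributed to the anchor, which is what the study sets out to report.

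The size is unknown: it is k/n, and the documents give no procedure-only rate from which to estimate k. Any effect on the success rate depends on how the case report form item was worded and completed, so no figure should be put on it. The conclusion rests on reading the worst-causality rule as one value across product and procedure, which is what its wording says.

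**What to change.** 1. In SAP 5.3.6.2, tabulate AEs and SAEs in three classes: related to the product (with or without the procedure), related to the procedure only, and related to neither. Split the ADE, SADE, USADE and ASADE rows into the first two classes, since an event related to neither is not an ADE under any of the definitions. Keep the pooled figure as an extra row, and give the by-causality summary for each relationship.
2. In the same section, replace the reference to study drug with a statement of which relationship a missing causality is assigned to.
3. In SAP 5.3.2, state that the device-related AE item uses the device relationship, as its wording says.
4. Reconcile protocol 12.1.2, Table 12.1-1 and SAP 5.3.6.1. A protocol amendment needs signatory and ethics committee approval under protocol section 15. If that is not wanted, state the working definition in the SAP and record it in 5.8.

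The cost is SAP wording and slightly longer tables. The split relies on device and procedure relationship being held as separate fields, as protocol 12.3 implies. The case report form should be checked first, because a single combined field would not support the split without going back to the sites.
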